10.3.3.2 Severity

Severity (as in mild, moderate, or severe headache) is not equivalent to seriousness, which is based on subject/event outcome or action criteria usually associated with events that pose a threat to a subject's life or functioning. The severity of each will be assessed using the defined categories in Table 10.3.3.2.1.

The Investigator will determine the severity of each AE and SAE and EOSI using the NCI CTCAE v4. Adverse events that do not have a corresponding CTCAE term will be assessed according to the general guidelines for grading used in the CTCAE v4 as stated below.

BOMARIN[°] 270-201 Amendment 10

Table 10.3.3.2.1: Adverse Event Grading (Severity) Scale

Grade	Description	
1	Mild: asymptomatic or mild symptoms; clinical or diagnostic observat indicated	ions only; intervention not
2	Moderate: minimal, local or noninvasive intervention indicated; limitin instrumental activities of daily living (ADL) ^a	ng age-appropriate
3	Severe or medically significant but not immediately life-threatening: h prolongation of hospitalization indicated; disabling; limiting self-care	
4	Life threatening or debilitating: consequences; urgent intervention indicated	Grade 4 and 5 AEs should always be
5	Death related to AE	reported as SAEs

^a Instrumental ADL refer to the following examples: preparing meals, shopping for groceries or clothes, using the telephone, managing money.

^b Self-care ADL refer to the following examples: bathing, dressing and undressing, feeding oneself, using the toilet, taking medications, not bedridden.

10.3.3.3 Causality

The Investigator will determine the relationship of an AE to the study drug and will record it on the source documents and AE CRF. To ensure consistency of causality assessments, Investigators should apply the guidance in Table 10.3.3.3.1.

270-201 Amendment 10

Relationship	Description	
Not Related	Exposure to the IP has not occurred	
	• OR	
	• The administration of the IP and the occurrence of the AE are not reasonably related in time	
	• OR	
	• The AE is considered likely to be related to an etiology other than the use of the IP; that is, there are no facts, evidence, or arguments to suggest a causal relationship to the IP.	
Related	• The administration of the IP and the occurrence of the AE are reasonably related in time	
	AND	
	• The AE could possibly be explained by factors or causes other than exposure to the IP	
	OR	
	• The administration of IP and the occurrence of the AE are reasonably related in time	
	AND	
	• The AE is more likely explained by exposure to the IP than by other factors or causes.	

Table 10.3.3.3.1: Causality Attribution Guidance

Factors suggestive of a causal relationship could include (but are not limited to):

- Plausible temporal relationship
- Absence of alternative explanations
- Rarity of event in a given patient or disease state
- Absence of event prior to study drug exposure
- Consistency with study product pharmacology
- Known relationship to underlying mechanism of study drug action
- Similarity to adverse reactions seen with related drug products
- Abatement of AE with discontinuation of study drug, and/or recurrence of AE with reintroduction of study drug

The investigator's assessment of causality for individual AE reports is part of the study documentation process. Regardless of the Investigator's assessment of causality for individual AE reports, the Sponsor will promptly evaluate all reported SAEs against

Proprietary and Confidential

BOMARIN[°] 270-201 Amendment 10

cumulative product experience to identify and expeditiously communicate possible new safety findings to investigators and applicable regulatory authorities.

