"A pharmaceutical form of an active ingredient or placebo being tested or used as a reference in a clinical trial, including a product with a marketing authorization when used or assembled (formulated or packaged) in a way different from the approved form, or when used for an unapproved indication, or when used to gain further information about an approved use" (from International Conference on Harmonisation of Technical Requirements for Registration of Pharmaceuticals for Human Use ICH Harmonised Tripartite Guideline: Guideline for Good Clinical Practice E6 [ICH E6]).

The terms "IP" and "study drug" may be used interchangeably in the protocol.

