including the early use of corticosteroids (ie, by Week 3 post-BMN 270 infusion). While the majority of ALT elevations responded rapidly to corticosteroids, given current interest in the field of AAV gene therapy for the use of non-steroidal approaches to managing or preventing ALT elevations, alternate non-steroidal systemic immunosuppressive agents have also been used to manage hepatic reactions where corticosteroids have proven to be ineffective or where high doses/and or prolonged exposure to corticosteroids have led to unwanted side effects. Overall, the literature and clinical experience with BMN 270 suggests that transient elevations in liver enzymes are expected following AAV-based gene therapy for the treatment for hemophilia A or B without any long-term concerns of hepatic injury (Manno 2006; Nathwani 2011; George 2016; Miesbach 2016; Pasi 2020).

At the highest dose tested in 270-201 (6E13 vg/kg), the majority of subjects achieved FVIII levels above 50 IU/dL at 52 weeks post-infusion. Subjects in that cohort also reported markedly decreased bleeding compared with pre-study rates and the ability to discontinue prophylactic FVIII infusions. Subjects at all dose levels continue to be followed.

In 270-301, an interim analysis has shown increased FVIII activity in the majority of subjects to mild HA or normal levels at 26 weeks post-infusion, also with markedly decreased bleeding compared with pre-study rates and the ability to discontinue prophylactic FVIII infusions. All subjects who were included in the 1-year analysis have been dosed with 6E13 vg/kg and continue to be followed.

The current data available has shown an established positive benefit-risk profile for BMN 270 at the 6E13 vg/kg dosing level. Given the monitoring measures in place in the clinical protocol(s) to minimize the risk to subjects participating in the existing studies, the identified risks are justified by the anticipated benefits that may be afforded to subjects. Each subject in 270-301 will have a comprehensive surveillance plan that monitors LTs during the study, and elevations in LTs will be addressed according to the guidelines set forth in the protocol. Safety will be assessed by adverse event reporting and clinical laboratory assessments.

For additional information on safety findings from clinical studies, refer to current version of the Investigator's Brochure.

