^a Reactive corticosteroids may be initiated when a subject's ALT value is \geq 1.5x ULN or based on review of FVIII and liver enzyme data after consultation between the Investigator and the Medical Monitor.

^b Following initiation or completion of steroid regimen, if ALT elevation $\geq 1.5x$ ULN is reported, steroid management decisions will based on discussions between the Investigator and Medical Monitor. Modification of the steroid regimen may take into consideration timing of the ALT elevation (after Week 52), as well as possible confounders for the ALT elevation and adverse events related to corticosteroid dosing. Guidance for tapering oral corticosteroids can be found in Section 9.4.8.2.

^c After discontinuation of corticosteroids, weekly labs for ALT and FVIII levels will be measured once a week for 4 weeks to ensure stability in values. If these assessments are already being done as part of normal study follow-up, they do not need to be duplicated.

^d Regardless of the assessments listed in the Schedule of Assessments (Table 9.1.2, Table 9.1.3, or Table 9.1.4), subjects initiated on corticosteroids will only be required to have laboratory evaluations on a weekly basis.

^e Should only be performed in subjects with a history of hepatitis B or hepatitis C prior to study entry.

270-201 Amendment 10

Table 9.1.7: Schedule of Events – Liver Biopsy Substudy

	Within 28 Days Before Biopsy Day	Within 7 Days Before Biopsy Day	1 Day Before Biopsy Day ^d	Biopsy Day (BD)
Informed Consent	X			
Liver Ultrasound ^a	X			
Brief Physical Examination	X		X	Х
Hematology, Coagulation, Chemistry Assessments ^b	X		X	
Liver Tests ^b	X		X	Х
FibroScan		Х		
Local FVIII Activity Level Assessment		Х	X	Х
Pre-Biopsy Consultation ^c		Х		
Liver Biopsy ^e				Х

^a Liver ultrasound must be performed within 28 days prior to the scheduled biopsy, unless an ultrasound result from the prior 3 months is already available.

^b Refer to Table 9.7.9.2.1 for laboratory assessments to be included, and to Table 9.7.9.3.1 for liver tests.

^c Subjects will undergo a pre-biopsy consultation with the investigator (treating hematologist).

^d Subjects may need to repeat/extend this visit if their FVIII activity levels need adjustment before the biopsy, at the discretion of the investigator (treating hematologist).

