9.3.4.1 Study Safety Evaluation Criteria

If any of the following events occur in a subject in the study who has received BMN 270 infusion, enrollment into the trial will be put on halt to complete an extensive safety analysis per Section 9.1.

• Any ALT elevation > 5x ULN for at least 2 consecutive weeks after administration of BMN 270, in the absence of a definitive alternate etiology for the increase

- The occurrence of Grade 3 or higher adverse events (excluding ALT elevation) assessed as related to study drug, including liver failure and clinical hepatitis
- The detection of neutralizing antibodies to hFVIII following BMN 270 infusion
- The detection of AAV vector DNA in the semen of a participant in 3 consecutive samples (which are at least 2 weeks apart) more than 52 weeks after BMN 270 infusion, as discussed in Section 9.7.9.7
- The occurrence of a malignancy excluding skin cancers at any point after BMN 270 infusion

If the following event occurs in a subject in the study who has received BMN 270 infusion, a DRB review and analysis of safety data will be undertaken to determine whether the enrollment into the trial will be put on halt:

• Grade 2 adverse event assessed as related to study drug that persists for at least 7 days

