14.6 Safety Analysis

The Medical Dictionary for Regulatory Activities terminology (MedDRA) will be used by the Sponsor to assign system organ class and preferred term classification to events and diseases, based on the original terms entered on the CRF.

All AEs will be coded using MedDRA. The incidence of AEs will be summarized by system organ class, preferred term, relationship to study drug, and severity. A by-subject listing will be provided for those subjects who experience a serious AE (SAE), including death, or experience an AE associated with early withdrawal from the study or study drug. Hepatitis is of interest, and the percentage of subjects who report hepatitis will be presented.

Clinical laboratory data will be summarized by the type of laboratory test. For each clinical laboratory test, descriptive statistics will be provided on Baseline as well as all subsequent visits. Descriptive statistics for physical examination results and vital signs will also be provided.

Detailed statistical methods will be provided in the SAP.

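### Causality is asked for BMN 270 only, in two overlapping categories, so adverse events caused by the protocol-directed corticosteroids cannot be identified as such

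*Protocol*

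**What the plan says.** Section 10.3.3.3 (Causality) fixes the object of the assessment: "The Investigator will determine the relationship of an AE to the study drug and will record it on the source documents and AE CRF". Section 4 (Definition of Terms) says "The terms 'IP' and 'study drug' may be used interchangeably in the protocol", so the question concerns BMN 270 and not other agents given under the protocol.

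Table 10.3.3.3.1 offers two answers. One route to Not Related is "The AE is considered likely to be related to an etiology other than the use of the IP", explained there as an absence of any fact, evidence or argument for a link to the IP. One route to Related is a reasonable time relation together with "The AE could possibly be explained by factors or causes other than exposure to the IP".

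Section 14.6 uses the answer: "The incidence of AEs will be summarized by system organ class, preferred term, relationship to study drug, and severity". Section 9.3.4.1 uses it too. One halting criterion is "The occurrence of Grade 3 or higher adverse events (excluding ALT elevation) assessed as related to study drug", and the DRB-review criterion for persistent Grade 2 events carries the same condition.

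The protocol also sets out and anticipates immunosuppression. Section 9.4.8.2.1 gives a default corticosteroid course for ALT elevation. Table 9.4.8.2.1.1 allows tacrolimus or mycophenolate in refractory or intolerant subjects. Footnote b of Table 9.1.6 lets the steroid regimen be modified in light of "adverse events related to corticosteroid dosing". Section 7.4 reports that high doses or "prolonged exposure to corticosteroids have led to unwanted side effects".

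**The concern.** Safety is a primary objective (Section 8), and the immunosuppression is given because of a reaction expected after the vector. A reader of the safety results will want to know how much harm came from the vector, how much from the agents given to control ALT, and how much from the two together. The protocol collects these events but asks a single causality question that does not mention those agents. The event must go into one of two categories that do not exclude each other.

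What is at stake is the meaning of the related-AE table. If steroid events go to Not Related, harm from treatment the protocol itself directs appears as background. If they go to Related, harm from the steroid appears as vector toxicity. If investigators differ, the table is a mixture that cannot be separated afterwards. An analysis plan can tabulate events by timing, but it cannot recover an investigator's attribution that was never recorded.

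**Working it through.** The point concerns a definition and a recording rule, so the check is mainly a reading of the sections against each other.

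1. **Object of the assessment.** Section 10.3.3.3 names the study drug, and Section 4 equates study drug with IP. Corticosteroids, tacrolimus and mycophenolate are not the IP. The protocol text names no second attribution.

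2. **Scope of collection.** Section 10.1.1 defines a reportable AE as one in a subject given the study drug or another protocol-imposed intervention, whatever the attribution. Section 9.4.8.2.1 sends all AEs to Section 10. Steroid AEs are therefore collected. Collection is wider than attribution.

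3. **A test case in Table 10.3.3.3.1.** Take a steroid-caused AE arising a few weeks after infusion.
   - Not Related, third route: another etiology is likely, so the event fits. The explanatory clause asks for no argument for an IP link. An investigator who regards the steroid as a consequence of the vector may say that there is one.
   - Related, first route: the event is reasonably related in time to the infusion and could possibly have another cause. Read literally, the event fits here too.
   - Both answers are available, although the section says that the table is meant to make assessments consistent.

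4. **Can timing separate the two causes?** Section 7.4 describes steroid use by Week 3 after infusion in the regimens it compares. Steroid exposure then overlaps the period when vector reactions are expected, so date of onset alone does not settle the cause.

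5. **Exposure.** Section 7.4 reports ALT elevation in most subjects given BMN 270. That is not a count of steroid-treated subjects in this trial, and initiation under Section 9.4.8.2.1 is discretionary. The two written courses are:
   - Section 9.4.8.2.1: 2+2+2+2+1+1+1 = 11 weeks, which reproduces the stated total. Cumulative dose, as weeks × 7 × mg/day: 840+560+420+280+105+70+35 = 2310 mg.
   - Table 9.4.8.2.1.1: 2+3+1+1+1 = 8 weeks. Cumulative dose: 840+840+210+140+70 = 2100 mg.

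   These totals show that a course is substantial. They count no adverse events. The two schedules differ and need reconciling, but this point does not depend on which applies.

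6. **Sensitivity of the summary.** Section 14.7 caps the trial at 15 dosed subjects. For a given preferred term, recoding one subject's only such event changes the related incidence by 1/15 = 6.7 percentage points. If Cohort 4 enrolled its planned maximum of 3+3 = 6, the change within that cohort is 1/6 = 16.7 points.

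**The case against.** The strongest case on the other side has five parts.

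- **The harm stays visible.** Section 14.6 summarises all AEs by system organ class, preferred term and severity. Section 10.5.1 requires SAEs and EOSI within 24 hours whether or not they are considered related. Section 10.3.3.3 has the sponsor evaluate every SAE regardless of the investigator's view. This stands: no event is lost, only its attribution.

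- **The direction is not fixed.** A reader might infer that every steroid-caused event must be coded Not Related, drops out of the related table, and makes the trial understate harm. The documents do not support that. The Not Related route carries its explanatory clause, and the first Related route admits a time-associated event with another possible cause. Either coding is open, so a one-directional bias is not shown.

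- **The eCRF and the SAP are not shown.** A steroid-relationship field may exist, and further tables are ordinary SAP content. This stands as a condition on the fix. It does not remove the defect in the protocol's own causality rule and table.

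- **Concomitant medication dates are on the CRF (Section 9.4.8),** so AEs during steroid exposure can be tabulated. That is true, but it gives timing and not cause. Footnote b of Table 9.1.6 can likewise operate through a discussion about one subject without any field.

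- **The Section 9.3.4.1 criteria govern enrollment.** The Amendment 9 rationale on consent says that recruitment is already complete, and under Section 15 the DRB reviews safety on an ongoing basis anyway. A reader might infer that a severe steroid reaction would now slip past a live stopping rule. The documents do not support that either, and what remains is an undefined term.

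**Conclusion.** The point holds in a limited form. The protocol asks for causality against BMN 270 only, through two categories that can both fit a steroid-caused event. AEs of the protocol-directed immunosuppression therefore cannot be identified as such, and the summary by relationship may omit them or mix them with vector events. Total AE and SAE reporting is intact.

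The number of affected events cannot be derived from the documents. The incidence shifts in step 6 are what one recoded subject would cause and are not estimates of actual error. The conclusion assumes that the eCRF has no separate steroid-attribution item. If it has one, only the overlapping categories and the use of that item in the safety summary remain. The change is worth making because the point bears on a primary objective and follow-up continues to Week 364, with steroid courses still possible after Week 52.

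**What to change.** 1. In Section 10.3.3.3 and on the AE eCRF, add a separate relationship item for corticosteroid or other immunosuppressant given for ALT elevation, unless the eCRF already has one.
2. Reword Table 10.3.3.3.1 so that Related and Not Related exclude each other, in particular for an event with a plausible time relation and a likely alternative cause.
3. In Section 14.6, report the incidence of AEs related to the vector, to the immunosuppressant, and to either, by dose cohort.
4. In Section 9.3.4.1, state whether related to study drug includes events attributed to protocol-directed immunosuppression. No new trigger is needed.

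The cost is one field, one table and a review of past events in at most 15 subjects. Much of that attribution would be retrospective and open-label, so it should be flagged as such and shown apart from prospectively recorded attribution. The combined treatment-attributable AE rate may look less favourable than the vector-only rate.

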10.4 Procedures for Recording Adverse Events

10.4.1 Recording Adverse Events on an eCRF

Investigators should use precise medical terminology when recording AEs or SAEs on the AE eCRF. Avoid colloquialisms and abbreviations.

Record only one diagnosis, sign, or symptom per event field on the AE eCRF (eg, nausea and vomiting should not be recorded in the same entry, but as 2 separate entries).

In order to classify AEs and diseases, preferred terms will be assigned by the Sponsor to the original terms entered on the AE eCRF, using MedDRA (Medical Dictionary for Regulatory Activities) terminology.

10.4.1.1 Diagnosis versus Signs and Symptoms

Using accepted medical terminology, enter the diagnosis (if known). If not known, enter sign(s) and/or symptom(s). If a diagnosis subsequently becomes available, then this diagnosis should be entered on the AE (or SAE, as appropriate) eCRF, replacing the original entries where appropriate.

10.4.1.2 Adverse Events Occurring Secondary to Other Events

In general, AEs occurring secondary to other events (eg, cascade events) should be identified by their primary cause. For example, if severe diarrhea is known to have resulted in dehydration, it is sufficient to record only diarrhea as an AE or SAE on the AE eCRF. However, medically important events that may be linked and/or separated in time should be recorded as independent events on the AE eCRF. For example, if severe haemorrhage leads to renal failure, both events should be recorded separately on the AE eCRF.

10.4.1.3 Persistent or Recurrent Adverse Events

A persistent AE (duration of adverse event > 7 days) is one that extends continuously, without resolution, between subject evaluation time points. Events that change in severity necessitate the recording of an additional AE. AEs that do not have a change in severity should be recorded only once on the eCRF.

A recurrent AE is one that occurs and resolves between subject evaluation time points, but then subsequently recurs. All recurrences of the AE should be recorded on the AE eCRF.

BIOMARIN[®] 270-2

10.4.1.4 Abnormal Laboratory Values

Laboratory test results will be recorded on the laboratory results pages of the AE eCRF, or appear on electronically produced laboratory reports submitted directly from the central laboratory, if applicable.

Any laboratory result abnormality fulfilling the criteria for a SAE or EOSI should be reported as such, and recorded in the AE eCRF. Any laboratory result abnormality of CTCAE Grade 4 or 5 should be recorded as an SAE in the AE eCRF, unless the abnormal laboratory results has been reported or captured as part of an underlying diagnosis.

A clinical laboratory abnormality is considered clinically significant and should be documented as an AE if not refuted by a repeat test to confirm the abnormality and **any** one or more of the following conditions is met:

- Accompanied by clinical symptoms
- Requiring a change in concomitant therapy (eg, addition of, interruption of, discontinuation of, or any other change in a concomitant medication, therapy or treatment).
- The abnormality suggests a disease and/or organ toxicity
- The abnormality is of a degree that requires active management (eg, change of dose, discontinuation of study drug, more frequent follow-up assessments, further diagnostic investigation, etc.)

This applies to any protocol and non-protocol specified safety and efficacy laboratory result from tests performed after the first dose of study medication that falls outside the laboratory reference range and meets the clinical significance criteria.

This does not apply to any abnormal laboratory result that falls outside the laboratory reference range but that does not meet the clinical significance criteria (these will be analyzed and reported as laboratory abnormalities), those that are considered AEs of the type explicitly exempted by the protocol, or those which are a result of an AE that has already been reported.

For purposes of this study, laboratory tests showing a decreased level of hFVIII activity should not be reported as adverse events unless there is an impact to clinical outcomes (eg, increased rate of bleeding, worsening of joint disease).

10.4.1.5 **Pre-existing Conditions**

A pre-existing condition is one that is present prior to administration of BMN 270. Such conditions should be recorded as medical history on the appropriate eCRF.

BOMARIN° 270-201 Amendment 10

A pre-existing condition should be recorded as an AE or SAE during the study **only** if the frequency, intensity, or character of the condition worsens during the study period. It is important to convey the concept that a pre-existing condition has changed by including applicable language in the verbatim description of the event (eg, *more frequent* headaches).

